11. ETHICAL CONSIDERATIONS	20
11.1. Ethical Approval	20
11.2. Protocol Amendments	20
11.3. Informed Consent	20
11.4. Risk – Benefit Analysis	20
A. Study Related Risks	20
B. Study Related Benefits	21
12. MONITORING PROCEDURES	21
12.1. Source Documentation	21
12.2. Direct Access	21
12.3. Site Qualification Visit	21
12.4. Site Initiation Visit	21
12.5. Interim Monitoring Visits	22
12.6. Closeout Visit	22
12.7. Sponsor Audits and Regulatory Inspection	22
12.8. Data Handling and Record Keeping Requirements	22

12.9. Data Recording and Record Retention	22
13. DEVIATIONS FROM PROTOCOL.....	23
13.1. Protocol Deviation Reporting Requirements	23
14. Publication policy.....	23
BIBLIOGRAPHY	24
Appendix 1	
JOURNEY II BCS and CR Component Part Numbers.....	28

ABBREVIATIONS & DEFINITIONS

AE	Adverse Event
ADE	Adverse Device Effect
AP	Anteroposterior
CAPA	Corrective and Preventive Action
CRO	Contract Research Organization
CRF	Case Report Form
EC	Ethics Committee
EQ-5D	EuroQuol 5D
FDA	Food and Drug Administration
FU	Follow-Up
GCP	Good Clinical Practice
ICF	Informed Consent Form
ICH	International Conference on Harmonisation of Technical Requirements for Registration of Pharmaceuticals for Human Use
IRB	Institutional Review Board
ITT	Intention to Treat Population
KSS	Knee Society Score
PI	Principal Investigator
PP	Per-protocol Population
QoL	Quality of life
SAE	Serious Adverse Event
SADE	Serious Adverse Device Effect
TKA	Total Knee Arthroplasty
USADE	Unanticipated Serious Adverse Device Effect

Protocol Synopsis:

Title of Study:	Clinical, Radiographic, and Patient-reported Outcomes associated with the use of the Navio [°] Robotic-assisted Surgical System in Total Knee Arthroplasty
Study Type:	Evidence Generation
Study Device:	Navio [°] Robotic-assisted Surgical System
Study Purpose:	To demonstrate superior accuracy with the Navio [°] Robotic-assisted Surgical System in achieving desired post-operative mechanical alignment, compared to TKA procedures using standard instruments, as well as to document clinical and patient-reported outcomes in subjects receiving TKA with the Navio [°] system.
Study Design:	Multicenter, prospective single-arm cohort study with historical control.
Primary Endpoint:	Post-operative Mechanical Alignment (percentage of subjects achieving target alignment, defined as $\pm 3^\circ$ from target) at one month post-operative.
Secondary Endpoints:	
 • Implant survival rate from baseline to 2 year end of study visit. • Knee Society Score 2011 • Quality of Life (EQ-5D) 5L • Forgotten Joint Score (FJS) • Hospital Length of Stay • Operative Time • Radiographic Assessments
Safety Endpoints	The number of occurrences and the frequency of subjects reporting: 
 • adverse events (AE) • serious adverse events (SAE) • adverse device effects (ADE) • serious adverse device effects (SADE) • unanticipated serious adverse • device effects (USADE) • device deficiencies (DevD)
Length of Study:	Approximately 3 years 
 • 1 year for enrollment and 2 years for follow-up
Number of Sites:	Approximately 6 sites
Sample Size:	120 subjects
Inclusion Criteria:	
 1. Subject requires primary total knee arthroplasty with the Journey II BCS or Cruciate-Retraining (CR) Systems due to degenerative joint disease

	
(primary diagnosis of osteoarthritis, post-traumatic arthritis, avascular necrosis, or rheumatoid arthritis).
 
 2. Subject was considered skeletally mature at the time of implantation (at least 18 years or older). 3. Subject agrees to consent to and to follow the study visit schedule (as defined in the study protocol and informed consent form) by signing the IRB/EC approved informed consent form. 4. Subject plans to be available through two (2) years postoperative follow-up.
Exclusion Criteria:	
 1. Subject has BMI ≥ 40. 2. Subject has condition(s) that may interfere with the TKA survival or outcome (i.e., Paget's or Charcot's disease, vascular insufficiency, muscular atrophy, uncontrolled diabetes, moderate to severe renal insufficiency or neuromuscular disease, or an active, local infection). 3. Subject is deemed by investigator to require a constrained or deep dish tibial insert. 4. Subject has inadequate bone stock to support the device (severe osteopenia, history of severe osteoporosis, or severe osteopenia). 5. Subject has mental or neurologic condition(s) that may pre-empt the ability or willingness to restrict activities. 6. Subject is 80 years of age or older. 7. Subject is a prisoner or impending incarceration.

1. BACKGROUND AND STUDY RATIONALE

1.1. Background

Total Knee Arthroplasty (TKA) has become an effective and reliable treatment for arthritis of the knee (1). TKA is associated with low morbidity and mortality, and its effectiveness in reducing joint pain and improving range of motion is well established. In 2014, over 750,000 knee replacements were performed in the US (2).

A significant innovation in TKA has been the introduction of computer navigation and robotic-assisted surgery (3). One such technology is the Navio[°] Robotic-assisted Surgical System. This system is a semi-autonomous image-free system. During the surgery, the surgeon maps the condylar landmarks and determines alignment indices to define the volume and orientation of bone to be removed. The tools to remove the bone and place the implants are controlled and manipulated by the surgeon with the guidance of a 3-dimensional digital map of the surgical surface.

Originally the Navio[°] system was launched for use in unicompartmental knee replacement only. To date, there have been over 1000 unicompartmental knee replacement surgeries using the system. In 2017, Smith & Nephew Inc. expanded the indications for the Navio[°] system to include TKA. The purpose of this multicenter, prospective study is to evaluate outcomes associated with this new indication.

1.2. Study Rationale

The purpose of this study is to demonstrate superior accuracy with the Navio[°] Robotic-assisted Surgical System in achieving desired post-operative mechanical alignment, compared to TKA procedures using standard instruments. An additional study purpose is to document clinical and patient-reported outcomes in subjects receiving TKA with the Navio[°] system.

2. STUDY OBJECTIVES

2.1. Primary Objective

The primary objective of this study is to demonstrate the superiority of the use of the Navio[°] Robotic-assisted Surgical System in the implantation of the JOURNEY[®] II BCS or CR Systems in achieving post-operative mechanical alignment within $\pm 3^\circ$ of target, as compared to TKA procedures using standard instruments.

2.2. Secondary Objectives

Secondary objectives of this study include the generation of safety, performance, and health economic evidence supporting the use of the Navio[°] Robotic-assisted Surgical System in TKA procedures, per the endpoints listed below.

3. STUDY ENDPOINTS

3.1. Primary Endpoint

Post-operative Mechanical Alignment (the proportion of subjects achieving post-operative mechanical alignment, defined as $\pm 3^\circ$ from target) at the 1 month study visit.

3.2. Secondary Endpoints

The following assessments will be collected at each follow up visit, as described in Section 7.1, Table 1, Schedule of Events.

- Implant survival rate from baseline to 2 year end of study visit.
- Knee Society Score 2011
- Quality of Life (EQ-5D) 5L
- Forgotten Joint Score (FJS)
- Hospital Length of Stay
- Operative Time
- Radiographic Assessments

3.3. Safety Endpoints

The number of occurrences and the frequency of subjects reporting: adverse events (AE), serious adverse events (SAE), adverse device effects (ADE), serious adverse device effects (SADE), unanticipated serious adverse device effects (USADE), and device deficiencies (DevD).

4. STUDY DESIGN

This is a multi-center, prospective cohort study with a comparison to historical control to collect 2-year safety and effectiveness data on 120 subjects, at approximately 6 sites in the United States, who have undergone Navio System-assisted TKA.

Subject data will be evaluated at the pre-operative, operative, one month, six months, one year, and two year follow up visits.

A final analysis will be conducted once all subjects have completed a two year visit.

5. STUDY DEVICE

The Smith & Nephew Navio Robotic-assisted Surgical System aids the surgeon in planning and executing a procedure involving bone preparation for prosthesis implantation. The system is comprised of computer-assisted surgical instrument control, a commercially available surgical drill, image-free navigation, and planning software with standard navigation technology.

The Navio System uses data gathered during the beginning of the surgical procedure (planning phase) to generate a computer model of the knee surface to be remodeled in preparation for the implant. The software uses data collected during the planning phase along with pre-loaded data describing the implant geometry to guide the surgeon in shaping the knee for the selected implant. The Navio system software then allows the surgeon to evaluate the range of motion and fit of the implant prior to finalizing the procedure.

The Navio system software consists of a patient and user management module, a surgical planner, and an intraoperative cutting module. The surgeon uses patient data collected at the surgical site to align the implant and shape the target surface of the bone to accept the intended implant. The Navio system also uses the tracked position of the surgical bur to control its cutting engagement to the bone that is to receive the implant. This cutting control is based on the bur's proximity to the planned target surface of the bone.

The cutting control is achieved in two ways:

- Exposure control adjusts the bur's exposure with respect to a guard. If the surgeon encroaches on a portion of bone that is not to be cut, the Navio system retracts the spinning bur behind the guard, disabling cutting. The Navio system software also adjusts the depth of the cut by adjusting the exposure of the bur outside of the bur guard.
- Speed control regulates the signal transmitted to the drill motor. This limits the speed of the spinning bur or disables bur motion entirely if the target surface has been reached. Bur motion is also disabled if the bur is moved outside of expected cutting boundaries.

The surgeon can alternate between these two cutting control modes. The surgeon can also disable both cutting control modes and operate the Navio system as a standard navigated drill.

The Navio system incorporates a detailed user interface that provides procedure setup, tracking status, visual indicators, and real-time cutting progress during the procedure.

The Navio System is shown below:

Description	Part Number
Tracking Camera and Stand	110001
Navio System Cart	NPFS-02000, -02010, -02020, -02070
Anspach Drill Foot Control	120041
Navio System Foot Control	100460
Navio System Handpiece	110137
Anspach Drill	101209

The function of each component is as follows:

- Tracking Camera and Stand - The mobile infrared tracking camera is used to determine the position of the point probe and the surgical bur tip and track their movement by scanning the position of reflective trackers relative to the position of trackers mounted on the patient's femur and tibia.
- Navio System Cart - The mobile cart contains the electronic control system, electrical system integration unit, computer, and uninterruptible power supply (UPS). Navio system carts are

available in 120 VAC and 220-240 VAC versions. The cart provides storage for the power cord, Anspach® drill foot control, and the Navio system foot control. The touchscreen monitor is the primary user interface for the Navio system.

- Anspach® Drill Foot Control - The Anspach drill foot control is used to control the Anspach drill during surgery. The surgeon must press the foot control to activate the bur. The speed of the bur is controlled by the Navio system software in speed control mode.
- Navio System Foot Control - The Navio system foot control is used as an alternative to the touchscreen monitor when data points are being collected to define landmarks, shape bone, and position the implant prior to surgery.
- Navio System Handpiece - The Navio system handpiece controls the position of the Anspach Drill and bur relative to the position of the guard and the desired profile of the bone being cut. In exposure mode, as the bur nears the target surface of the bone intended to accept the implant, the Anspach drill and bur retracts into the guard to prevent further cutting of bone.

The Navio system is intended to assist the surgeon in providing software-defined spatial boundaries for orientation and reference information to anatomical structures during orthopedic procedures. The system is indicated for use in surgical knee procedures, in which the use of stereotactic surgery may be appropriate, and where reference to rigid anatomical bony structures can be determined. These procedures include UKR and patellofemoral arthroplasty. The Navio System is indicated for use with cemented implants only (refer to User Manuals for more detail).

5.1. Surgical Technique

The Navio System is to be used per standard of care at the participating study sites. Each participating investigator will have performed a minimum of 8 Navio TKA procedures prior to enrolling subjects on this study. The Navio System is indicated for Smith & Nephew cemented Total Knee implants, but for the purposes of this study we are restricting the type of implant to the Journey II BCS or Cruciate-Retraining (CR) Systems and compatible S&N patellar implants. The list of acceptable part numbers can be found in Appendix 1. The patella must be resurfaced during the primary TKA procedure.

6. STUDY POPULATION

6.1. Subject Screening & Enrollment

To eliminate the potential for selection bias, Investigators should screen all subjects undergoing a Navio® assisted TKA. In order to do so, only the existing information obtained per standard routine medical procedures will be used. No study-specific screening procedures, activities or questionnaires will be performed during pre-screening.

Once a subject has completed the informed consent procedure and signed the Informed Consent Form, the Principle Investigator (PI), or delegated study research staff, can complete the screening process with the subject. All potential subjects who undergo the screening process will be documented on a Screening and Enrollment Log, on which reasons for exclusion from or denial to participate should be noted. In the event that a subject has a bilateral Navio assisted TKA, only the first knee treated after informed consent will be enrolled in the study.

6.2. Subject Inclusion Criteria

Subjects must meet the following inclusion criteria to be included in the study:

1. Subject requires primary total knee arthroplasty with the Journey II BCS or Cruciate-Retraining (CR) Systems due to degenerative joint disease (primary diagnosis of osteoarthritis, post-traumatic arthritis, avascular necrosis, rheumatoid arthritis).
2. Subject was considered skeletally mature at the time of cone implantation (at least 18 years or older.)
3. Subject agrees to consent to and to follow the study visit schedule (as defined in the study protocol and informed consent form) by signing the IRB/EC approved informed consent form.
4. Subject plans to be available through two (2) years postoperative follow-up.

6.3. Subject Exclusion Criteria

Subjects will be excluded from the study if they meet any of the following exclusion criteria:

1. Subject has BMI ≥ 40 .
2. Subject has condition(s) that may interfere with the TKA survival or outcome (i.e., Paget's or Charcot's disease, vascular insufficiency, muscular atrophy, uncontrolled diabetes, moderate to severe renal insufficiency or neuromuscular disease, or an active, local infection).
3. Subject is deemed by investigator to require a constrained or deep dish tibial insert.
4. Subject has inadequate bone stock to support the device (severe osteopenia, history of severe osteoporosis or severe osteopenia).
5. Subject has mental or neurologic condition(s) that may pre-empt the ability or willingness to restrict activities.
6. Subject is 80 years of age or older.
7. Subject is a prisoner or impending incarceration.

7. STUDY PROCEDURES

7.1. Study Schematic

The intervals and schedule of events are provided in Table 1.

Schedule of events (*as needed)	Preop	Op/DC	1 Month	6 Months	1 Year	2 Years
Visit Window	-28 days	0	30±7 days	182±30 days	365±60 days	730±60 days
Informed Consent	✓					
Inclusion/Exclusion	✓					
Demographics/Medical History	✓					
Operative Data Collection		✓				
Discharge Data Collection		✓				
Mechanical Alignment on Long Leg X-rays	✓		✓			
Standard AP, Lateral, and Patellar (Skyline or Merchant) X-rays				✓	✓	✓
2011 Knee Society Score	✓		✓	✓	✓	✓
Quality of Life (EQ-5D-5L)	✓		✓	✓	✓	✓
Forgotten Joint Score (FJS)	✓		✓	✓	✓	✓
Adverse Event Assessment		✓	✓	✓	✓	✓
End of Study/Exit		*	*	*	*	*

* if applicable

7.2. Pre-Operative Visit

Procedures to be completed at the pre-operative visit:

- Confirm informed consent
- Assign a subject study number
- Inclusion/Exclusion
- Demographics and medical history
- 2011 Knee Society Score
- Quality of Life (EQ-5D)
- Forgotten Joint Score
- Perform long leg X-rays to assess Mechanical Alignment

7.3. Surgery

Procedures to be completed at the time of surgery:

- Update information in the Screening and Enrollment Log
- Operative Data including target mechanical alignment
- Discharge Data
- Adverse Event Assessment

7.4. One Month Post-Operative Visit

- Perform long leg X-rays to assess Mechanical Alignment
- 2011 Knee Society Score
- Quality of Life (EQ-5D)
- Forgotten Joint Score
- Obtain and record any AEs occurring from the time of study device implantation
- Adverse Event Assessment

7.5. Six Months, One Year, Two Years Post-Operative

- Perform standard AP, lateral, and patellar X-rays
- 2011 Knee Society Score
- Quality of Life (EQ-5D)
- Forgotten Joint Score
- Obtain and record any AEs occurring from the time of study device implantation
- Adverse Event Assessment
- Collect End of Study Information if applicable

8. SUBJECT COMPLETION AND DISPOSITION

8.1. Screening

Subjects considered potential candidates for the study based on pre-screening will sign an IRB/EC approved Informed Consent Form (ICF) prior to any study activities. The PI, or delegated study research staff, may then complete the first study visit with the subject.

8.2. Enrolled Subject

Subject enrollment occurs at the time of surgery. Every subject that has signed consent, is assigned a Subject ID, and received a total knee implant from the Journey II family with surgical assist from the study device will be considered enrolled in the study.

8.3. Conditions for Study Termination

All reasonable efforts should be made to retain the subjects for the 2 year duration of this study. If the subject has a revision of any component, the subject will be terminated from the study.

A. Screening Failure

If a subject has provided consent, completed screening and for any reason is not operated on by the study device and does not receive a total knee implant from the Journey II BCS or Cruciate-Retraining (CR) Systems, the subject will not be considered enrolled in the study.

For these subjects an Inclusion/Exclusion and Informed Consent CRF, Demographics CRF, Medical History CRF, and End of Study CRF need to be completed. However, the CRFs should not be submitted into the Sponsor's database unless the subject signed consent and was assigned a Subject ID.

B. Voluntary Withdrawal

Study participation is voluntary and subjects may withdraw at any point during the study without giving their reason for doing so. An End of Study CRF will be completed for all subjects who do not finish the study, and reason for withdrawal will be documented in the form.

C. Lost to Follow-Up

Some actively enrolled subjects may not return for follow-up exams due to a variety of reasons. Study personnel must make reasonable efforts to contact the subject and document the following contact attempts prior to declaring a subject to be lost to follow-up: the subject has been contacted according to the site's policies, but no less than 2 documented phone contacts and 1 certified letter without response. Copies of all attempts to reach the subjects per regular mail or email and/or the attempts to contact the subject via other means should be documented and that documentation should be kept with the subjects CRF at the site. A subject will be considered lost to follow-up if he/she does not appear for the scheduled study visit for 2 consecutive visits and study personnel are unable to contact the subject.

D. Study Termination by Investigator/Sponsor

The Investigator **may** withdraw subjects from the study for many reasons, including but not limited to the following:

- subject noncompliance to study schematic
- subject lost to follow-up

The Investigator **should** withdraw subjects from the study:

- in case any component of the original Journey II hardware is revised/exchanged
- if the Investigator or the Sponsor stops the study for any reason

For each case, information will be obtained on the End of Study CRF, detailing circumstances leading to the withdrawal.

E. Pregnancy

If during the course of the study a subject becomes pregnant, study procedures that are contraindicated during pregnancy and/or lactation (e.g. X-Rays) will not be obtained; however, the subject will continue to be followed for study visits and information will be collected regarding the outcome of the birth.

F. Study Site Discontinuation

A specific study site in this multicenter study may also warrant termination under the following conditions:

- non-compliance to Good Clinical Practice (GCP) or protocol
- failure to enroll subjects
- major protocol deviations
- inaccurate or incomplete data
- unsafe or unethical practices
- safety or performance considerations
- investigator involuntarily discontinues participation in study

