9. SAFETY REPORTING

Adverse events and device deficiencies, noted by study staff and reported by the subject, and occurring from the time of study device implantation through study completion should be recorded on the appropriate CRFs and reported as below.

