10.4. Analysis Populations

All subjects that are operated on by the study device are considered study participants. The following study populations and analysis sets will be defined:

- **Safety Population:** This population will include all subjects that received the study device and will be used for analysis of demographics, disposition data and safety.
- **Modified Intention to Treat Population (mITT):** Following the intention to treat principle, this population Full Analysis Set (FAS): This will include all subjects that received the study device and attended at least one post-baseline assessment. This population will be used for the primary analysis of all efficacy endpoints.
- **Per Protocol Population (PP):** This population will include all subjects that received the study device, meet the inclusion/exclusion criteria, attend all follow-up assessments within the specified window, and have no significant protocol deviations. Subjects that are required to be withdrawn from the study under the protocol (e.g. due to revision) will be included regardless of attendance of follow-up visits unless they are deemed to have significant protocol deviations or failed to meet the inclusion/exclusion criteria. This population will be used as secondary analysis of all efficacy endpoints.

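### Sections 8.2, 8.3.A and 10.4 do not give one rule for who is enrolled and analysed, and an abandoned Navio procedure can fall out of the primary denominator and out of safety collection

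*Combined protocol and SAP*

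**What the plan says.** Three sections of the protocol decide membership, each by a different test.

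- Section 8.2 places enrolment at surgery. A subject with consent and a Subject ID who "received a total knee implant from the Journey II family with surgical assist from the study device will be considered enrolled in the study". Both the implant and the assistance are required.
- Section 8.3.A defines the screening failure. It covers the subject who "is not operated on by the study device and does not receive a total knee implant from the Journey II BCS" or CR systems. Both must be missing.
- Section 10.4 opens with: "All subjects that are operated on by the study device are considered study participants". There is no implant condition.

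Section 10.4 then builds the analysis sets on receipt of the study device. For Safety: "This population will include all subjects that received the study device and will be used for analysis of demographics, disposition data and safety". For the mITT set, which carries the primary analysis: "This will include all subjects that received the study device and attended at least one post-baseline assessment". The study device is a surgical instrument, and the protocol does not define what it means to have received it.

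On data collection, section 9 covers adverse events and device deficiencies "occurring from the time of study device implantation through study completion should be recorded on the appropriate CRFs". The forms listed in 8.3.A for a non-enrolled subject are the eligibility and consent form and then: "Demographics CRF, Medical History CRF, and End of Study CRF need to be completed". None of these is an operative, alignment or adverse event form.

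**The concern.** The primary objective (section 2.1) is to show that Navio reaches target alignment more often than standard instruments. A Navio procedure that is begun and then given up may be a failure of the system under test. If such a subject is not enrolled, the observed proportion describes only procedures that Navio completed, and it is compared with a fixed 73.4%. In a single-arm study no concurrent group has matching exclusions to offset this.

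The case is foreseeable. Section 5 says that the surgeon can switch off both cutting-control modes and use the system as a navigated drill, so partial use has no stated boundary. Exclusion criterion 3 depends on the investigator's view of the insert needed, and nothing says what happens if that need first appears during surgery.

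Safety is also at stake. Deficiencies in abandoned procedures say a good deal about the device, yet they may arise before any implantation in a subject for whom no adverse event form is listed.

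**Working it through.** **Step 1. The rules side by side.**

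| Case | 8.2: enrolled? | 8.3.A: screening failure? | 10.4: participant? |
|---|---|---|---|
| Navio completed, Journey II BCS/CR | yes | no | yes |
| Navio completed, other implant | no | no | yes |
| Navio started then abandoned, Journey II BCS/CR | unclear | no | unclear |
| Navio not started, Journey II BCS/CR | no | no | no |
| Navio not started, other implant | no | yes | no |

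Row 2 is a direct conflict between 8.2 and 10.4. Row 3 has no answer, because neither assistance from the device nor being operated on by it is defined for partial use. Row 4 is a gap between 8.2 and 8.3.A. There is a smaller mismatch as well: 8.2 speaks of the Journey II family, 8.3.A of the BCS and CR systems only.

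**Step 2. The plan's success rule.** Inputs: reference 292/398 = 73.4% and expected proportion 88% (10.1); exact two-sided 95% limits, with success if the lower limit exceeds 73.4% (10.5); 120 recruited with 5% lost, so 120 × 0.95 = 114 evaluable, against 115 stated (10.1). The exact lower limit for x aligned of n is the 2.5% quantile of Beta(x, n − x + 1).

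- 93/114: 73.23%, not met.
- 94/114: 74.21%, met. This is the pass mark at 114.
- At n = 115 the pass mark is also 94. The chance of success is 98.2% at a true 88%, not the stated 80%. That is a separate matter; the question here is bias, not power.

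**Step 3. Worst case at the pass mark.** Return excluded subjects to the denominator, all counted as not aligned:

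- one: 94/115, lower limit 73.45%, still met;
- two: 94/116, lower limit 72.71%, not met.

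**Step 4. Near the planned result.** 101/115 = 87.8%, lower limit 80.4%.

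- nine added: 101/124, lower limit 73.48%, met;
- ten added: 101/125, lower limit 72.79%, not met.

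**Step 5. Effect on false success.** The number excluded is an assumption, since the documents give none. Let k of 115 be excluded, all of whom would have been unaligned, with a true proportion of 73.4% over all 115. The proportion among those analysed is then 0.734 × 115/(115 − k).

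| k | True proportion in those analysed | Pass mark | Chance of declaring superiority |
|---|---|---|---|
| 0 | 73.4% | 94/115 | 2.4% |
| 3 | 75.4% | 92/112 | 5.6% |
| 6 | 77.4% | 90/109 | 12.0% |

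**Step 6. A milder assumption.** If six of 115 are converted and align at the reference rate, the overall proportion is (109 × 0.88 + 6 × 0.734)/115 = 87.2%, against 88.0%. The shift is small.

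**The case against.** A reader might infer four stronger things, and the documents do not support them.

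- **That all three sections contradict one another.** Sections 8.2 and 8.3.A do not: mixed cases simply fit neither. The one direct conflict is 8.2 against 10.4.
- **That subjects given Navio and another implant are lost from Safety.** The analysis sets are defined in 10.4, which read literally keeps them. Losing them requires 8.2 to override 10.4, and no section says that it does. Device deficiencies in any component of the study device are reportable (9.1.F), section 7.3 lists an adverse event assessment at surgery, and the screening log leaves a trace. What remains is the abandoned procedure, which 10.4 itself leaves unclear. A log entry does not replace an adverse event or deficiency record.
- **That membership is chosen with the endpoint known.** The endpoint is read from the 1-month long-leg film, which does not exist at surgery. Only the intraoperative course is known. Conditioning on that can still bias the proportion.
- **That the trial result is likely to turn on this.** At a true 88%, the chance of success with 114 subjects is 97.0%; adding two unaligned subjects lowers it to 94.8%. So two such exclusions decide the outcome about 2.2% of the time.

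It is also fair to say that a change of implant need not reflect on Navio at all, and that the primary objective is limited to Journey II BCS and CR. Subjects given another implant therefore should not be forced into the primary set.

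**Conclusion.** The concern holds in this form: 8.2 and 10.4 conflict for Navio with another implant, and no section classifies a Navio procedure that is started and then abandoned. If 8.2 is the gate and assistance is read as completed assistance, abandoned procedures leave the primary denominator because of an intraoperative event, and their safety data may go uncollected. The direction tends to favour Navio.

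The size cannot be fixed from the documents, which give no conversion rate. Two excluded subjects are enough at the pass mark and ten near the planned 88%, in both cases assuming that every excluded subject was unaligned. If conversions align at about the reference rate, the effect is under one percentage point for six subjects. This is a rule to settle before the data are seen; it does not show that the planned result is unsafe.

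**What to change.** - Use one rule in 8.2, 8.3.A and 10.4: every consented subject in whom the Navio procedure is started (first tracker pin or registration) is enrolled and in the Safety set. Define receipt of the study device the same way.
- Define screening failure as Navio not started, and name the same implant systems in 8.2 and 8.3.A.
- Keep subjects with a Journey II BCS or CR implant whose Navio procedure was abandoned in the primary set, analysed by their 1-month film. Add a sensitivity analysis that counts them as not aligned.
- Keep subjects given another implant in Safety and report them separately.
- Start recording of adverse events and device deficiencies at the start of the Navio procedure.

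The cost is protocol wording, a few more subjects in the denominator and in follow-up, and possibly a slightly lower success rate.
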